6.4.2.2. Conversion to Abnormal TCD

- For subjects who withdraw from the study or reach analysis data cutoff date without an event (ie, TCD flow velocity reaching abnormal range), their time to conversion to abnormal will be censored at the date of last TCD assessment prior to study withdrawal or analysis data cutoff date, as applicable (Section 8.2.2.2, Table 2).

6.4.2.3. TCD Responder

A TCD responder is defined as a TCD flow velocity reduction from Baseline ≥ 15 cm/sec, and will be assessed separately at Week 24, Week 48, and Week 96.

- Subjects with a missing TCD flow velocity value at the assessment timepoint will be classified as non-responders.
- Subjects initiating HU postbaseline are to be discontinued from the study. TCD assessments obtained after HU initiation will be excluded from analysis (considered missing).
- RBC transfusions: TCD results within 8 weeks after the transfusion date will be imputed for the analysis of TCD response. Post transfusion results will be imputed by data from the most recent study visit prior to the transfusion (including Baseline) with a non-missing TCD value.

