2. INTRODUCTION

The purpose of Study GBT440-032 (C5341021) is to evaluate the effect of voxelotor on reducing the risk of stroke, as measured by transcranial doppler (TCD) flow velocity in subjects 2 to < 15 years of age with sickle cell disease (SCD) who have conditional TCD flow velocity at baseline.

This document describes the statistical methods to be used in the summary and analysis of data from Study GBT440-032. Population pharmacokinetic (PK) analyses will be described in a separate document. Descriptive statistics for **CCI** may be summarized in a separate report. Where this document differs from the study protocol, the methodology described in the SAP is considered the latest and supersedes the corresponding section(s) in the protocol.

As of 1 May 2024, study drug dosing in GBT440-032 was voluntarily paused by the Sponsor due to a safety imbalance. Study visits and other study activities continued in accordance with the protocol. Subsequently, a decision was made by the Sponsor on 25 September 2024 to terminate the study based on the totality of clinical data for Oxybryta (voxelotor) and the last subject last visit occurred subsequently.

[figure not shown]

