6.3. Analysis Timing

The primary study analysis was performed after all randomized subjects completed the study through Week 48 or discontinued early, and all data through a corresponding data cut-off date (determined based on the last subject's Week 48 visit date) was entered in the database, reviewed, and verified. This included formal evaluation of the primary Week 24 efficacy endpoint, secondary Week 24 and Week 48 efficacy endpoints, and summary of all safety data through the data cut-off date. Summaries of Week 96 and time to event efficacy endpoints based on partial data available at this time were considered exploratory.

A final study analysis will be performed after the last subject's last visit and final study database lock. Summaries of Week 96 and time to event efficacy endpoints based on partial data will be considered exploratory due to the early termination of the study. The estimated treatment effects (voxelotor vs. placebo) and corresponding 95% CIs will be presented for these endpoints, but without formal hypothesis testing.

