7. ANALYSIS POPULATIONS

The following populations will be considered in the analysis of data. Assignment or exclusion of subjects from the analysis populations will be performed prior to study unblinding.

- Intent-to-Treat (ITT) Population: the ITT population includes all randomized subjects. This is the primary analysis population for efficacy, demographics, baseline characteristics, and disposition data. Subjects will be grouped according to the treatment group to which they are randomized.
- Safety Population: All subjects who receive at least 1 dose of study treatment will be included in the safety population. This is the primary analysis population for safety and exposure data. Subjects will be grouped according to the study treatment they receive.

090177e1a2bf4d41Approved\Approved On: 31-Jan-2025 17:16 (GMT)

- **PK Population:** The PK population will consist of all subjects who receive active study drug and have at least 1 measured concentration at a scheduled PK time point after the start of dosing. If any subjects are found to be noncompliant with respect to dosing or have incomplete data, protocol violations, or clinical events that affect PK, a decision will be made on a case-by-case basis as to their inclusion in the analysis. Subjects in this population will be used for all PK summaries.

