8.2.2.3. TCD Response Endpoint

The TCD responder endpoint, defined as a TCD flow velocity reduction from Baseline \geq 15 cm/sec at Week 24, Week 48, or Week 96, will be analyzed using an exact Cochran-Mantel-Haenszel (CMH) general association test stratified by the randomization stratification factors for the treatment difference between voxelotor and placebo. The difference in percent

090177e1a2bf4d41\Approved\Approved On: 31-Jan-2025 17:16 (GMT)

responders between treatment groups with corresponding 95% CI using the Mantel-Haenszel stratum weight method will be presented. The analysis will be performed separately for each timepoint of interest. Missing data will be handled per Section 6.4.2.3, with subjects with a missing value at the assessment timepoint classified as non-responders.

For the analysis of TCD response at Week 24, the average of TCD values at Week 24 and Week 28 will be used as a sensitivity analysis. If the TCD assessment is missed at one time point, the TCD value at the other (non-missing) time point will be used. Subjects with missing TCD values at both Week 24 and Week 28 timepoints will be classified as non-responders.

In addition, a sensitivity analysis will be performed to assess an alternative TCD response definition based on a TCD flow velocity reduction from Baseline ≥ 30 cm/sec. Analyses will be performed separately for the Week 24, Week 48, and Week 96 time points.

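### In the final analysis, the exploratory Week 96 responder estimates count children whose Week 96 TCD is missing only because the sponsor ended the study as non-responders, which shrinks the reported difference toward zero

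*SAP*

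**What the plan says.** SAP 6.4.2.3 defines a TCD responder by a fall from baseline of at least 15 cm/sec, which "will be assessed separately at Week 24, Week 48, and Week 96". Its missing-data rule is "Subjects with a missing TCD flow velocity value at the assessment timepoint will be classified as non-responders". SAP 8.2.2.3 repeats it: "with subjects with a missing value at the assessment timepoint classified as non-responders". Neither section distinguishes reasons for missingness.

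The effect measure is absolute. SAP 8.2.2.3 says the difference in percent "responders between treatment groups with corresponding 95% CI using the Mantel-Haenszel stratum weight method will be presented". It adds a 30 cm/sec definition with no missing-data rule of its own, and says "Analyses will be performed separately for the Week 24, Week 48, and Week 96 time points"; the general rule therefore appears to apply there too. SAP 8.2 bases efficacy on the ITT population, and in SAP 7 "the ITT population includes all randomized subjects".

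On study closure, SAP 2 reports that dosing was paused from 1 May 2024 while visits continued, and that "a decision was made by the Sponsor on 25 September 2024 to terminate the study". SAP 6.3 says of the final analysis: "Summaries of Week 96 and time to event efficacy endpoints based on partial data will be considered exploratory due to the early termination of the" trial. It still plans to present treatment effects and 95% CIs, without formal testing.

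**The concern.** A child who was still in follow-up when the study closed, and had not reached Week 96, has no Week 96 TCD for a reason unrelated to response. The rule scores that child as a treatment failure. Such children add to the denominator and can never add to the numerator, so both rates and their difference fall. The CI is then narrow around the diluted value.

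The SAP handles the same child differently elsewhere. In time to conversion, a child without an event is censored at the last TCD (SAP 6.4.2.2 and Table 2). In change from baseline, missing values after discontinuation for reasons other than abnormal TCD are not imputed (SAP 6.4.2.1). Only the responder analysis turns the missing visit into a failure.

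The version history suggests an oversight. The rule entered in version 2.0 (11 Jan 2024), before the pause and termination. Version 3.0 adapted several sections to those events, but its change summary lists neither 6.4.2.3 nor 8.2.2.3. What is at stake is the interpretation of the longest-term response estimate: a reader comparing Week 48 with Week 96 could take a loss of denominator for a loss of effect.

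**Working it through.** **The plan's own figures.** The SAP gives no planned response rate or power for Week 96 response. Its primary power does reproduce: difference 15 cm/sec, SD 24 and about 89 per arm after 20% dropout from 112 give 98.6%, against a stated figure above 95%.

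**Dilution formula.** Let f be the fraction able to reach Week 96, equal in both arms and unrelated to response. Let r1 and r0 be the response rates that would be seen if all could reach it. The SAP rule reports f·r1 and f·r0, so the reported difference is f·(r1 − r0). Equal f is reasonable because randomization is 1:1 in permuted blocks, so the arms should share nearly the same calendar.

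**Inputs.** There are 112 children per arm (SAP 6.1). Assumed, because the documents give neither: f from 0.2 to 0.6, and r1 = 45%, r0 = 20%. The CIs are unstratified Wald intervals, a simplification of the Mantel-Haenszel weighting in SAP 8.2.2.3:

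- SAP rule: half-width = 1.96·√{[f·r1(1 − f·r1) + f·r0(1 − f·r0)]/112}
- Restricted to reachable children: half-width = 1.96·√{[r1(1 − r1) + r0(1 − r0)]/(112f)}

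At f = 0.4 under the SAP rule: √[(0.18×0.82 + 0.08×0.92)/112] = √(0.2212/112) = 0.0444, and 1.96×0.0444 = 0.087. Restricted: √[(0.45×0.55 + 0.20×0.80)/44.8] = √(0.4075/44.8) = 0.0954, and 1.96×0.0954 = 0.187.

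| f | Rates under SAP rule | Difference, points (95% CI) | Restricted difference (95% CI) |
|---|---|---|---|
| 0.2 | 9% vs 4% | 5 (−1.4 to 11.4) | 25 (−1.4 to 51.4) |
| 0.4 | 18% vs 8% | 10 (1.3 to 18.7) | 25 (6.3 to 43.7) |
| 0.6 | 27% vs 12% | 15 (4.8 to 25.2) | 25 (9.7 to 40.3) |

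**Second set of rates.** Suppose instead that the planning values (15 cm/sec, SD 24) hold at Week 96, with normal changes and no mean change on placebo. Response is then Φ(0) = 50.0% versus Φ(−15/24) = 26.6%, a difference of 23.4 points. The SAP rule reports 23.4×0.6 = 14.0, 23.4×0.4 = 9.4 and 23.4×0.2 = 4.7 points. The shrinkage factor is the same.

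**Calendar.** A child is at Study Day N on 25 Sep 2024 if randomized N − 1 days earlier. From SAP Table 1:

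- Day 631 (analysis window opens): 630 days earlier, 4 Jan 2023
- Day 665 (protocol visit range opens): 664 days earlier, 1 Dec 2022
- Day 679 (protocol visit range closes): 678 days earlier, 17 Nov 2022

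The documents give no enrolment dates or exact last-visit date, so f cannot be computed.

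**The case against.** The strongest reply is that little depends on this. Week 96 response is not in the test sequence of SAP 8.2.6, nor in that of protocol 8.4.3. SAP 6.3 labels Week 96 results partial and exploratory, and SAP 8.1 tabulates discontinuation reasons by arm. The Week 96 change-from-baseline estimate is not subject to this rule. All of that stands, and it limits the point to an exploratory estimate. It does not make the estimate right: the SAP still presents the difference with a 95% CI, and a partial-data label does not say that unreached visits were counted as failures. Partial data might be read as limiting the table to children who could reach Week 96, but no section sets that denominator and SAP 7 says all randomized.

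Second, the size rests on assumed inputs. That also stands. A reader might infer that the CI always misses the true difference. It does not: at f = 0.6 it runs from 4.8 to 25.2 and includes 25. Nor would a risk ratio move under equal f (45/20 = 18/8 = 2.25), but the SAP reports a difference.

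Third, a reader might infer that any fall in response from Week 48 to Week 96 merely reflects closure. The documents do not support that. Visits continued after the 1 May 2024 pause, so some Week 96 values could come from children up to about 21 weeks off drug by 25 Sep 2024 (147 days). The post-pause exclusion in SAP 8.2.8 covers only change from baseline, so this second possible source of lower response remains.

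Fourth, changing a denominator after the Week 48 analysis is post hoc. That is fair. The proposed restriction uses only randomization date, which is fixed before treatment and unrelated to outcome, and the all-randomized table can be kept beside it.

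**Conclusion.** The rule is wrong as written for the Week 96 responder estimates in the final analysis, at both 15 and 30 cm/sec. The direction follows from the SAP's own rule, denominator and effect measure, given that some children lost Week 96 to termination and that this was balanced by arm and unrelated to response. The size is unknown: the reported difference is f times the true one, for example 5 to 15 points instead of 25 for f from 0.2 to 0.6 under the assumed rates.

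A wider reading is not supported. SAP 6.3 places the Week 24 and Week 48 analyses after every child had completed Week 48 or discontinued early, so termination does not create this problem there. No formally tested result changes. The Week 96 summaries at the Week 48 data cut-off were already produced, so an edit can reach only the final analysis.

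**What to change.** In SAP 6.4.2.3 and 8.2.2.3, for the final analysis:

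- Limit the Week 96 responder analyses (15 and 30 cm/sec) to children who, by randomization date alone, could have completed the protocol Week 96 visit range (to Day 679) before one stated study-closure date. If 25 Sep 2024 is that date, this means randomized by about 17 Nov 2022.
- Within that set, keep scoring missing values as non-response, including for children who stopped early.
- Keep the all-randomized version, if wanted, as a supplementary table, and report missing Week 96 counts by arm and reason.
- State that some Week 96 values may have been taken after the 1 May 2024 dose pause, so lower response may also reflect time off drug.

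Using the opening of the analysis window (Day 631) as the cut-off would leave part of the problem. Children randomized after about 1 Dec 2022 and up to 4 Jan 2023 would be kept although they had not reached Day 665 by 25 Sep 2024.

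The cost is a short SAP addition and one flag derived from randomization date. The CI widens (at f = 0.4, from about ±8.7 to ±18.7 points), which reflects the information available. The denominator is set after the Week 48 analysis and should be reported as such. Week 24 and Week 48 stay as written.

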6.4.2.4. Hemoglobin and Hemolysis Change from Baseline

- For the primary method of analysis of these endpoints (MMRM), missing at random (MAR) will be assumed.
 - For change from baseline in Hb, a sensitivity analysis using last observation carried forward (LOCF) for subjects that discontinue the study early due to conversion to abnormal TCD flow velocity will also be performed.
- Subjects initiating HU postbaseline are to be discontinued from the study. Assessments of Hb and clinical measures of hemolysis obtained after HU initiation will be excluded from analysis.
- RBC transfusions: all laboratory results within 8 weeks after the transfusion date will be imputed for the MMRM change from baseline analysis of Hb and hemolysis measures. Post transfusion results will be imputed by data from the most recent Study

090177e1a2bf4d41Approved\Approved On: 31-Jan-2025 17:16 (GMT)

Visit prior to the transfusion (including Baseline) with a non-missing laboratory value.

6.4.3. Imputation of Incomplete Dates

An incomplete date is any date for which either the day, month, or year is unknown, but all three fields are not unknown. For analyses which require a complete date, the following imputation will be used. For data listings, any partial dates will be displayed in the listing without imputation (eg, JAN2023, 2021).

6.4.3.1. Start Dates for Concomitant Medications

- For missing start day only – Day will be imputed as the first day of the month (ie, 1) with the following exception: If the partial date falls in the same month and year as the treatment start date then the concomitant medication start date will be imputed as the treatment start date.
- For missing start day and month – Day and month will be imputed as the first day of the year (ie, 1 January) with the following exception: If the partial date falls in the same year as the treatment start date then the concomitant medication start date will be imputed as the treatment start date.

6.4.3.2. Start Dates for Adverse Events when the Event Occurs Prior to the First Dose

- For missing start day only – Day will be imputed as the first day of the month (ie, 1) with the following exception: If the partial date falls in the same month and year as the treatment start date then the AE start date will be imputed as the day prior to the treatment start date.

6.4.3.3. Start Dates for Adverse Events when the Event is Not Prior to the First Dose

- For missing start day only – If the partial date falls in the same month and year as the treatment start date then the adverse event start date will be imputed as the treatment start date. Otherwise, the day will be imputed as the first day of the month (ie, 1) as long as the imputed date does not occur before the treatment start date.

7. ANALYSIS POPULATIONS

The following populations will be considered in the analysis of data. Assignment or exclusion of subjects from the analysis populations will be performed prior to study unblinding.

- Intent-to-Treat (ITT) Population: the ITT population includes all randomized subjects. This is the primary analysis population for efficacy, demographics, baseline characteristics, and disposition data. Subjects will be grouped according to the treatment group to which they are randomized.
- Safety Population: All subjects who receive at least 1 dose of study treatment will be included in the safety population. This is the primary analysis population for safety and exposure data. Subjects will be grouped according to the study treatment they receive.

090177e1a2bf4d41Approved\Approved On: 31-Jan-2025 17:16 (GMT)

- **PK Population:** The PK population will consist of all subjects who receive active study drug and have at least 1 measured concentration at a scheduled PK time point after the start of dosing. If any subjects are found to be noncompliant with respect to dosing or have incomplete data, protocol violations, or clinical events that affect PK, a decision will be made on a case-by-case basis as to their inclusion in the analysis. Subjects in this population will be used for all PK summaries.

8. STATISTICAL METHODS

8.1. Subject Disposition, Demographic, and Baseline Characteristics

The number of subjects randomized will be tabulated by country, study site, and treatment group. Subject disposition will be presented for all subjects in the ITT population. The number of subjects who completed the study and discontinued early from the study will be provided. The reasons for early discontinuation at any point also will be presented by treatment group. Additionally, the number of weeks on study will be summarized for all treated subjects.

Demographic data and baseline disease characteristics including age, sex, race, ethnicity, SCD genotype, Baseline Hb, Baseline HbF, Baseline hemolysis measures, Baseline (Screening) TCD flow velocity, Baseline HU use, and Baseline EQ-5D-Y (self-assessment, proxy) will be summarized using descriptive statistics. Subjects who record more than one race will be grouped into a single category denoted as multi-racial. This information will be reviewed for baseline differences between treatment groups, but no formal statistical testing will be performed.

Medical/surgical history will be coded using the Medical Dictionary for Regulatory Activities (MedDRA), and summarized descriptively.

Prior and concomitant medications (see Section 5 for definitions) will be coded using the World Health Organization (WHO) Drug Dictionary for the entire period of the study, and summarized descriptively.

8.2. Efficacy Analyses

Efficacy analyses will be based on the ITT patient population (Section 7), with subjects grouped according to the treatment assigned at randomization. Data from all randomized subjects, regardless of adherence to study drug or to the protocol will be included in the efficacy analyses. This includes data from subjects who discontinued study drug early but continued with study assessments.

Covariate Adjustment

Unless otherwise noted, analyses of primary and secondary efficacy endpoints will be adjusted (see Section 8.2.1 and Section 8.2.2) for the following randomization stratification variables:

- Baseline HU use (yes; no)
- Age (2 years to \leq 8 years; $>$ 8 years to $<$ 15 years)
- Screening TCD value (170 cm/sec to $<$ 185 cm/sec; 185 cm/sec to $<$ 200 cm/sec)

Note: The randomization stratification variable of geographic region (Africa including MENA; rest of world) as stated in the protocol is not included as a covariate as the vast majority of enrolled subjects are from a single region (Africa including MENA).

For stratification variables, the value recorded in the clinical database (ie, per case report form [baseline HU use and age] or by the central reading center [Screening TCD flow velocity]) will be compared to value captured in the IXRS. If differences are observed, the values from the clinical database will be used in the analysis.

Statistical Tests

All statistical tests will be conducted at a two-sided alpha level of 0.05. Adjustment for multiple comparisons is described in Section 8.2.6.

8.2.1. Primary Endpoint

The primary analysis of change from Baseline in TCD flow velocity to Week 24 will be performed using mixed model for repeated measures (MMRM). Independent variables will include treatment, study visit, treatment by study visit interaction, and randomization stratification factors (ie, HU use, age, and Screening TCD flow velocity). Within-subject variability will be modeled using an unstructured covariance matrix. A single model will be fit incorporating available TCD flow velocity data from all timepoints, including to Week 96.

Missing data will be handled per Section 6.4.2.1. Specifically for subjects who discontinued from the study due to conversion to abnormal TCD flow velocity, missing TCD values post abnormal TCD assessment will be randomly imputed. All post-baseline TCD values ≥ 200 cm/sec observed in the study for subjects with abnormal TCD will be used as the reference distribution. Multiple imputation based on re-sampling from the reference distribution will be used. For each iteration, the imputed TCD data will be combined with the observed data, and the combined augmented dataset analyzed using the primary analysis MMRM methodology described in this section. This will be repeated 100 times and the results will be combined using Rubin's rules (Little, et al [2012] and Little and Rubin [2002]). A seed of 440032 will be used.

The primary analysis is the comparison of treatments at Week 24 for voxelotor versus placebo. The Kenward-Roger correction for denominator degrees of freedom, standard errors, and test statistics will be utilized. Sample SAS code for the MMRM will be similar to the following:

```
PROC MIXED;  
  CLASS subject treatment visit agegrp HU BTCD;  
  MODEL ChgTCD = treatment visit treatment*visit agegrp HU BTCD/ DDFM=KR;  
  REPEATED visit / SUB=subject TYPE=un;  
  LSMEANS treatment*visit / DIFF CL E OM;  
RUN;
```

Note: agegrp, HU, and BTCD are per definition of stratification factors for randomization. If there are convergence issues with the statistical model, a compound symmetry covariance matrix will be used.

The adjusted mean (lsmean) of change from baseline in TCD at each visit, with the estimated standard error and 95% confidence interval (CI), will be estimated from the MMRM model for each imputed augmented dataset. Results from the multiple imputed datasets will be combined using Rubin's rules, and results will be presented by treatment group in tabular and graphic

format. The difference in the adjusted means between treatment groups and the associated 95% CI of the difference will be provided.

For the primary endpoint, subgroup analyses will be performed to evaluate the consistency of results across pre-specified subgroups (see Section 8.2.7).

In addition, sensitivity analyses will be performed to evaluate the robustness of results to missing data assumptions (see Section 8.2.8).

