6.4.2.1. TCD Change from Baseline

- For subjects discontinued from the study due to conversion to abnormal TCD flow velocity, missing TCD values post abnormal TCD assessment will be imputed using multiple imputation (MI). All post-baseline TCD values ≥ 200 cm/sec observed in the study for subjects with abnormal TCD will be used as the reference distribution for MI. This approach avoids the need to make a parametric assumption on the missing data given observed values, and appropriately accounts for variation due to “fill-in” missing values. See Section 8.2.1 for details.
 - A sensitivity analysis using worst observed value carried forward (WOCF) for subjects that discontinue the study early due to conversion to abnormal TCD flow velocity will also be performed (Section 8.2.8).

090177e1a2bf4d41\Approved\Approved On: 31-Jan-2025 17:16 (GMT)

- For all other subjects that discontinue the study early, missing TCD data will not be imputed.
- Subjects initiating HU postbaseline are to be discontinued from the study. TCD assessments obtained after HU initiation will be excluded from analysis.
- RBC transfusions: TCD results within 8 weeks after the transfusion date will be imputed for the MMRM analysis of TCD change from baseline. Post transfusion results will be imputed by data from the most recent study visit prior to the transfusion (including Baseline) with a non-missing TCD value.

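### The SAP sets no end date for imputing converters' TCD values; read literally, this leaves a small upward bias in the exploratory arm means after Week 48

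*SAP*

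**What the plan says.** SAP 6.4.2.1 states: "For subjects discontinued from the study due to conversion to abnormal TCD flow velocity, missing TCD values post abnormal TCD assessment will be imputed", by multiple imputation. SAP 8.2.1 repeats that "missing TCD values post abnormal TCD assessment will be randomly imputed" and names the source of the draws: "All post-baseline TCD values ≥ 200 cm/sec observed in the study for subjects with abnormal TCD will be used as the reference distribution". For everyone else, 6.4.2.1 states: "For all other subjects that discontinue the study early, missing TCD data will not be imputed".

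The analysis model reaches to the last visit: "A single model will be fit incorporating available TCD flow velocity data from all timepoints, including to Week 96". On the covariance, 8.2.1 says: "Within-subject variability will be modeled using an unstructured covariance matrix", with compound symmetry as the fallback if the fit does not converge.

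The SAP Introduction reports that dosing was paused on 1 May 2024, that "a decision was made by the Sponsor on 25 September 2024 to terminate the study", and that the last visit came after that decision. SAP 6.3 says that Week 96 and time-to-event summaries "based on partial data will be considered exploratory due to the early termination of the study"; estimates and 95% CIs are still presented, without tests. The formal sequence in 8.2.6 is the Week 24 change, the Week 48 change and the Week 24 response rate.

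Neither 6.4.2.1 nor 8.2.1 gives a last visit or calendar date for the imputation. The summary of changes for version 3.0 ties edits in 6.3, 8.2.6 and 8.2.8 to the dose pause or the termination. It lists none in 6.4.2.1 or 8.2.1.

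**The concern.** When a study closes early, values are missing at later visits for an administrative reason that plausibly has nothing to do with outcome. The literal imputation rule undoes that. A converter receives values of 200 cm/sec or more at every remaining visit to Week 96, including visits that no child could have attended. A child who had not converted when the study closed has nothing at those visits. Having a Week 96 value then depends partly on having converted, and converters have high velocities.

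At stake are the adjusted means at Weeks 60 to 96, which 8.2.1 sends to tables and graphs for each visit, and the Week 96 treatment effect with its 95% CI. Labelling these exploratory removes the test but not the estimate.

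**Working it through.** **1. The plan's own figures.** SAP 6.1 assumes 35% placebo conversion by Week 96, a hazard ratio of 0.5, 112 per arm and 20% drop-out.

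- Voxelotor conversion: 1 − 0.65^0.5 = 0.194.
- Events: 112 × (0.35 + 0.194) × 0.8 = 48.7, matching the stated 49.
- Log-rank power (Freedman): √49 × (1 − 0.5)/(1 + 0.5) − 1.96 = 0.373, which gives 64.6%, matching the stated 65%.

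These figures do not test the point, but they supply the conversion rates used below.

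**2. Converters' share of Week 96 rows.** Let f be the fraction of children who reach Week 96 before closure. The documents do not give f, so a range is shown. If all converters are imputed to Week 96 and only a fraction f of the others are observed, the converters' share is p / [p + (1 − p) f].

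- f = 1: 35% placebo, 19% voxelotor.
- f = 0.75: 0.35/(0.35 + 0.4875) = 42%; voxelotor 24%.
- f = 0.5: 0.35/(0.35 + 0.325) = 52%; voxelotor 32%.
- f = 0.25: 0.35/(0.35 + 0.1625) = 68%; voxelotor 49%.

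In simulation the placebo shares are slightly lower (about 49–51% and 65–66% for the last two rows), because some later converters are closed out first.

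**3. What reaches the reported means.** Row shares are not weights in the mixed model, which conditions late visits on each child's earlier values. A simulation of 20,000 children per arm fitted arm-specific visit means and an unstructured covariance by maximum likelihood. It compared the literal rule with imputation only at visits due before closure. Assumptions:

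- TCD at Weeks 24, 28, 48, 72 and 96 (the schedule table is unreadable, so Week 72 is a guess);
- baseline uniform on 170–200 cm/sec and SD of change 24;
- between-child share of variance 0.3 or 0.6;
- conversion 35% and 19.4%;
- uniform follow-up from Week 48 upward;
- no other drop-out and no stratification covariates.

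| f | Rise in raw Week 96 mean (cm/sec) | Excess in model mean per arm, literal vs capped rule (cm/sec) |
|---|---|---|
| 0.75 | about 2 | 0.1–0.4 |
| 0.5 | 5–6 | 0.5–0.8 |
| 0.25 | 11–12 | 1.1–1.7 |
| 0.1 | not summarised here | 1.9–3.7 |

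The model therefore removes roughly 85–90% of the raw distortion at f = 0.5 and 0.25. The remainder arises because a normal model does not fully describe a mixture of children held at 200 or more and everyone else. Both arms move upward, so the arm difference shifts by at most about 0.4 for f of 0.25 or more. At f = 0.1 it shifts by 1.2–1.4 toward zero. Compound symmetry gave Week 96 means of similar size.

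A second simulation, with TCD every 12 weeks and placebo conversion of 21–38%, gave Week 96 bias against full follow-up of 0.2–1.0 per arm at f = 0.5 and 0.6–2.1 at f = 0.25, with the difference moving 0.4 or less. Capping left −0.17 to 0.18.

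**4. Weeks 24 and 48.** SAP 6.3 says every child had reached Week 48 or left before the primary analysis. In the simulation Week 24 was unchanged and Week 48 moved by about 0.1 cm/sec or less.

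**5. Sensitivity analyses in 8.2.8.** WOCF and tipping point change the size of the imputed values, not which visits receive one, so neither tests this. The post-dose-pause exclusion drops later observed values of ongoing children while converters' imputed values stay, which widens the imbalance.

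**The case against.** The SAP is silent here. It never says that visits after closure are imputed, and a programmer could reasonably hold that a visit that never fell due is not a missing value. That stands: the defect is an unlimited rule, and the bias follows only if it is applied as written.

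A reader might take the row shares of 52% or 68% as the size of the bias. They are not. Conversion is seen in earlier TCD values, so the missingness is largely explained by data in the model, and most of the imbalance is corrected.

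A reader might also infer that the efficacy conclusions are compromised. The documents do not support this, because the formal tests concern Weeks 24 and 48 and Week 96 is declared exploratory. The shift is also small against sampling error. With 56 per arm at Week 96 (half of 112), a simple standard error of the difference is 24 × √(2/56) = 4.5 cm/sec, so 0.4 is under a tenth of it. Per arm it is 24/√56 = 3.2, against a bias of about 1 or less.

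Finally, a cap needs a date, and study end is not a single date here. 25 September 2024 is when the decision was made, and the last visit came later. If the last-visit date were used, children closed out earlier would stay missing while converters were still imputed. This also stands, and the fix has to deal with it.

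What remains is an avoidable, one-directional error in estimates that will be reported, which no planned analysis would reveal.

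**Conclusion.** The point holds as a minor one. SAP 6.4.2.1 and 8.2.1 give the converter imputation no end date. Applied literally, they over-represent converters at late visits and leave a small upward bias in exploratory arm means after Week 48. At Week 96 this is roughly 0.1–1 cm/sec per arm if half or more of the children reach the visit, and up to about 2 if a quarter do. The arm difference moves by about 0.4 or less in those cases, against a target effect of 15. Larger shifts appear only if about a tenth reach Week 96, and nothing in the documents shows that to be the case.

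These sizes rest on assumed enrolment timing and an assumed TCD schedule. The main Week 24 and Week 48 results are essentially unaffected. One point stays open: if any child had not reached Week 48 when dosing was paused, the post-dose-pause exclusion analysis could be touched at Week 48 too. The documents do not settle it.

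**What to change.** State in 6.4.2.1 and 8.2.1 that a converter's visit is imputed only if its target date is on or before one defined administrative date, and that later visits stay missing for all children.

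- **Primary analysis:** use the data cut-off. Since 6.3 describes this analysis as already done, record which limit was applied.
- **Final analysis:** use a stated study-closure date, chosen to reflect when ongoing children stopped having scheduled TCD visits, rather than the decision date or the last visit by default.
- **WOCF and tipping point:** apply the same limit.
- **Post-dose-pause exclusion:** use the dose-pause date as the limit, so that converters and ongoing children stop contributing together.

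The cost is a sentence or two in the SAP and one date check in the imputation program. There will be slightly fewer values, and so slightly wider CIs, at Weeks 60 to 96. If the program already works this way, the wording simply records it.
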